15 PUBLICATION POLICY

DAIDS and DTHF policies will govern publication of the results of this study. Any presentation, abstract, or manuscript will be submitted to DTHF and DAIDS for review prior to submission.

16 APPENDICES

16.5 HIV PRE/POST-TEST COUNSELING PROCEDURES (INCLUDING HIV TESTING ALGORITHM)

HIV Counseling Procedures

For HIV testing within the study, where the consent for study participation includes HIV testing, written consent for each individual HIV test within the study need not be obtained, however verbal consent should be confirmed. Pre and post test counseling is always performed.

Pretest counseling:

[figure not shown]
- a) The counseling staff deliver pre-test counseling, which includes:
 - An explanation of the test, and the window of infection with a negative test;
 - Basic information on HIV transmission and prevention
 - The significance of the potential test result
 - A reminder that although their test result is confidential, should the result be positive, staff will encourage the adolescent to share their result with a trusted adult
 - Discussion regarding who the participant might share their result with if positive
 - An explanation that a participant may be infectious even if their test result is negative.
- b) The staff member evaluates the psychological stability of the participant and the possible impact of testing positive at the pre-test visit.

Post-test counseling:

[figure not shown]
- a) If the result is negative, the counseling staff:
 - Discusses protection during the window period of a negative test; and
 - Discusses HIV test intervals, as appropriate.
 - Provides risk reduction counseling (see below)

- b) If the result is indeterminate, the counseling staff discusses its significance with the participant. A repeat test is performed.
- c) If the participant's result is positive, a second rapid test is performed. If this is positive, blood is drawn for a confirmatory laboratory test and a CD4 count. If the second rapid test result is negative, a confirmatory laboratory test should also be performed.
- d) If a positive result is confirmed:
 - The counseling staff/study physician shares the participant's result with them in a sensitive and neutral manner, allowing them time for the information to be understood and absorbed
 - The counseling staff/study physician discusses the difference between HIV and AIDS, treatment options, transmission issues, and the risks and benefits of partner notification, as well as the risks and benefits of notifying a trusted adult and how this might be done.
 - If this occurs at screening, the counseling staff/study physician explains to the participant that inclusion in study is not possible and refers the participant to a service provider/ clinic for further evaluation, management and support.
 - If a participant tests positive at any other visit, they can remain in the study and complete all study activities as planned including continuing to receive the vaccine (if they have consented to receive it). Further visits for psychosocial support and clinical management should be planned with the participant, per site-specific procedures.
 - Personalized referral to services for long term clinical management, and follow-up to ensure adolescent attendance should take place
 - Details of any community support groups and other relevant organizations should be passed on to the participant

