7.10 PROCEDURES FOR PARTICIPANTS WHO TEMPORARILY HOLD OR DISCONTINUE STUDY PRODUCT

7.10.1 Participants Who Become Infected with HIV

If a participant becomes HIV-infected at any time after enrolment into the study, the study product will be immediately terminated (if applicable) and the protocol-specified visit schedule will be followed, for participants who choose to be maintained in the study. In addition, extra interim visits will be added to their schedule for psychosocial support, if needed. These visits will occur in addition to study visits, although they can be combined with regularly-scheduled study visits.

If a participant tests positive on two rapid HIV antibody rapid tests, they will be considered HIV-infected and will receive post-test counseling on these results. Participants with an indeterminate

HIV test result will be asked to provide a blood sample for ELISA testing, to confirm whether they are HIV-infected.

Participants will be allowed as much time and given as much support as they need to cope with the positive result. The counselor disclosing the result will encourage the participant to identify a trusted adult (not necessarily the parent/ guardian) that they would like to disclose to. If necessary, this adult will be called into the clinic to help support the participant [see Section 16.5 for more detail, including the HIV testing algorithm].

The participant will also be given a referral letter for counseling and support in the community. The participant will also be reassured that they can return to the clinic at any time during clinic hours for support. Clinic staff will make telephone contact with the service to which they are referring the participant.

If both rapids are positive blood will be sent for confirmatory viral load testing. When these results are available the participant will be recalled and following another pretest information session, a blood sample for CD4 count as well as resistance and genotype testing will be obtained. The participant will be followed up at the study site for the duration of the study, and will receive a CD4 count at 3-monthly intervals and psychosocial support for disclosure, to ensure that initial care and counselling is well-managed. After the Final Study Visit, the research team will link the participant into long-term HIV care and treatment at one of the existing local health facilities.

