9.6 MANAGEMENT OF HIV INFECTION

Refer to Section 7.10.1 for specific study procedures regarding participants who become infected with HIV at any time during the study.

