9.7 CRITERIA FOR DISCONTINUATION

The criteria for permanent discontinuation of further study product for an individual participant are:

- Product-related toxicity (see Section 9.1)
- Requirement for prohibited concomitant medications
- HIV infection
- Pregnancy/lactation
- Completion of study as defined in the protocol
- Request by participant to terminate study product
- Any conditions or clinical reasons that will threaten safety and well-being of participant

The criteria for premature discontinuation of further study participation for an individual participant are:

- Lost to follow up as per site SOP
- Participant repeatedly non-compliant with study product as prescribed
- Pregnancy/lactation
- Request by participant to withdraw from study
- Request of the primary guardian or caregiver if s/he thinks the study is no longer in the best interest of the participant
- Participant judged by the Site Investigator to be at significant risk of failing to comply with the provisions of the protocol as to cause harm to self or seriously interfere with the validity of study results
- At the discretion of the Independent Ethics Committee, Medicine Control Council, Site Investigator, or pharmaceutical supporter.
- DAIDS, NIAID, the Office of Human Research Protection (OHRP), and the FDA as regulatory entities may also discontinue the study at their discretion.

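### Appendix 16.5(d) lets a participant who tests HIV-positive carry on with the study without excepting FTC/TDF, which is inconsistent with the stop rule in Protocol 7.10.1 and 9.7

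*Protocol*

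**What the plan says.** Four places in the Protocol deal with what happens to study product after a positive HIV test.

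- **Section 7.10.1** covers infection at any time after enrolment and says that "the study product will be immediately terminated (if applicable"). The participant may stay on the visit schedule. The section then refers the reader onward: "see Section 16.5 for more detail, including the HIV testing algorithm".
- **Section 9.6** has no rule of its own: "Refer to Section 7.10.1 for specific study procedures regarding participants who become infected with HIV at any time during the study".
- **Section 9.7** opens a list with "The criteria for permanent discontinuation of further study product for an individual participant are", and HIV infection is on it. Its second list, for ending study participation, does not include HIV infection.
- **Appendix 16.5, post-test item (d)**, under the lead-in "If a positive result is confirmed", first deals with screening. It then says of a positive test at any other visit that "they can remain in the study and complete all study activities as planned including continuing to receive the vaccine", with a bracketed condition that the participant agreed to have it. FTC/TDF is not mentioned, and there is no reference back to 7.10.1 or 9.7.

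Section 6.3.1 adds that the pharmacist dispenses only to participants with a negative HIV result.

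**The concern.** A counsellor with a newly positive participant is likely to be working from Appendix 16.5, because 7.10.1 and Section 14 both send staff there. The appendix says that everything scheduled continues, and its only example is an intervention that goes on being given. It says nothing about stopping tablets. Stopping two-drug PrEP in an infected adolescent is the purpose of the rule in 7.10.1 and 9.7, so the procedure for that conversation should state the rule or at least not cut across it.

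The route through Section 14 makes this slightly worse. That section points to 16.5 twice, and those references work. For the procedures that apply to infected participants it points to Section 7.8.1, which does not exist; Section 7.8 is the list of laboratory evaluations.

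**Working it through.** No arithmetic applies. The check is a comparison of texts.

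1. **Who is covered.** Item (d) of 16.5 applies to a positive test at any visit except screening. Section 7.10.1 applies to infection after enrolment. They overlap at every follow-up visit. Read literally, 16.5(d) also takes in the enrolment visit, where a positive test makes the person ineligible under inclusion criterion 5 in Section 5.2.

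2. **Could the two texts describe different stages of diagnosis?** No. Under 7.10.1, after two positive rapid tests "they will be considered HIV-infected and will receive post-test counseling on these results". Item (d) applies once the result is confirmed. Product should therefore already be off when 16.5(d) comes into play, and a difference in diagnostic status does not explain the difference in wording.

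3. **Staying in the study.** Both texts allow it, and 9.7 does not make infection a reason to leave. There is no conflict here.

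4. **Study product.** Section 7.10.1 stops it immediately and 9.7 permanently. Item (d) lets all activities go ahead and excepts nothing. This is the inconsistency.

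5. **What the vaccine is.** The only vaccine given here is hepatitis B, for non-immune participants (Sections 7.1 and 7.10.3). Section 5.3 excludes a seronegative candidate who refuses it, so the bracketed condition about agreeing to receive it fits poorly. It is not impossible, since the last dose falls at week 24 and immune participants receive none. The sentence may have been carried over from a vaccine study or may mean hepatitis B; the documents do not settle which. On either reading FTC/TDF is left unaddressed.

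6. **Which text governs.** Sections 7.10.1, 9.6, 9.7 and 6.3.1 agree with one another and are specific to study product. Section 4.3 also makes a negative HIV test a condition for continuing or restarting. The appendix stands alone against them.

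**The case against.** The strongest reply is that the conflict is inferred from silence. Item (d) never names FTC/TDF, and 7.10.1 itself keeps infected participants on the visit schedule, so *as planned* can be read to include the planned stop. The stop is also secured in several places, and 16.5 is a counselling text, not the section that governs product. Most of this stands. It makes the risk small, but it does not make the sentence right. The appendix does not say that the stop is part of the plan, its one example points the other way, and 7.10.1 names it as the place for more detail.

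A reader might infer more than the documents support:

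- **That the protocol orders tablets to continue after infection.** It does not. The sentence fails to except product and never directs that it be taken.
- **That tablets already held would go uncollected, so that leftover doses could be counted.** Section 6.3.1 leaves retrieval of unused product to site SOPs, which are not available for review, and 6.3.2 has the pharmacist document returns. Section 7.6 applies the week 48 procedures when the investigator stops product, and under 7.4 these include pill counts. No retrieval gap is shown, and a tablet count would not measure the fault in 16.5(d).
- **That the order of disclosure is contradictory.** Section 7.10.1 counsels on two positive rapids and also says "If both rapids are positive blood will be sent for confirmatory viral load testing", while 16.5 lists sharing the result after confirmation. The difference is only implied, because 16.5 does not restrict sharing to confirmed results. The flow charts in 16.6 and 16.7 survive only in part in the text reviewed, so nothing can be said about what they add.

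**Conclusion.** The point holds as a wording inconsistency with a safety bearing. A sentence in the cited counselling procedure does not fit this trial, leaves FTC/TDF unaddressed after a positive test, and is at odds with 7.10.1 and 9.7. The governing rule is clear and new dispensing is blocked, so the practical risk is small, provided that staff apply the body of the protocol. It cannot be quantified from the documents.

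Two further inferences should be resisted. The first is a material resistance risk. Section 2.6.7 reports resistance in participants already infected at enrolment in earlier trials and none among those infected during iPrEx, which gives no estimate for this setting. The second is damage to the analyses. The HIV incidence analysis dates seroconversion from the last negative and first positive tests, and nothing in this point alters those tests.

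**What to change.** Replace the sentence in 16.5(d) with wording such as: *A participant whose test is positive at any visit after enrolment may stay in follow-up; study product is stopped immediately and permanently (7.10.1, 9.7), and unused tablets are returned under the site SOP (6.3.1).* Starting the scope after enrolment leaves a positive test at enrolment to the eligibility criteria. In the same amendment, change the reference to 7.8.1 in Section 14 to 7.10.1.

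Leave the termination rule in 7.10.1, the order of disclosure, the testing algorithm and the SAP as they are. In particular, do not soften immediate termination to a temporary hold, which would weaken a rule that is already sound. The cost is one replaced sentence and one corrected cross-reference, with no new tests, visits or data.

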16.6 HIV Algorithm for Screening and Enrolment

16.7 HIV Algorithm for Follow-up visits

2nd Confirmatory Test

Positive – Confirmed HIV- Infected inform Protocol Chair

Indeterminate/ Negative - Consult with Protocol Chair for next steps

16.8 RISK REDUCTION COUNSELING PROCEDURES

Risk Assessment

a) The counseling staff member assesses the individual's risk factors for acquiring infection, including:

- Sexual activity
- Type of sex (vaginal, anal, oral)
- Reasons for being in a sexual relationship
- Number of sex partners (casual and steady) and sexual activities
- Sex with someone known to be HIV positive
- Sex with someone more than 2 years older or younger
- Sharing needles or having sex with someone who shares needles
- History of STI's and having sex with someone who has a history of STI's, especially genital lesions;
- Sex in exchange for drugs, money or other inducements
- Use of substances (e.g. alcohol) in connection with sexual activities
- Condom use

b) Included in the risk assessment, should be an assessment of the participant's knowledge of modes of HIV transmission and the impact of risk taking behaviors. Basic information on HIV transmission and prevention; this should focus on, but not be limited to, areas identified during risk assessment where knowledge was incomplete

c) The counseling is focused on the participant's individual risk factors and situation.

d) The counseling staff member and participant set manageable goals for risk reduction.

e) At each visit, the counseling staff member and the participant reassess the participant's behavior and risk factors, and if necessary, adjust the goals.

[figure not shown]
Risk reduction counseling for those who are HIV positive

Where participants have just learnt of their HIV-positive status, their immediate concerns may not be regarding risk reduction. It may be more appropriate to provide in depth risk reduction counseling (as above) at further visits.

Nonetheless, it is important to convey to adolescents that they are most infectious in the first few months after becoming HIV infected and should therefore take steps to protect others. In addition, they may be more susceptible to other STIs and it is therefore important that they protect themselves. This information at least should be communicated at the same visit where they learn of their HIV-positive status.

16. 9

Expedited Adverse Event Reporting Requirements for Pluspills:

1.“Life-threatening” refers to an event in which the patient was at risk of death at the time of the event. It does NOT refer to an event that hypothetically might have caused death if it were more severe.

² Per the ICH SAE definition, hospitalization is NOT an adverse event (AE), but is an outcome of the event. **DO NOT REPORT:** Any admission unrelated to an AE (e.g., for standard labor/delivery, cosmetic surgery, administrative or social admission for temporary placement for lack of a place to sleep); protocol-specified admission (e.g., for a procedure required by protocol); admission for diagnosis or therapy of a condition that existed before receipt of study agent(s) **and** has not increased in severity or frequency as judged by the clinical investigator. (**NOTE:** A new AIDS-defining event in a subject already known to be HIV-infected would be considered an increase in severity of a pre-existing condition [HIV infection] and **would be** reportable.)

³ Clinically insignificant physical findings at birth, including those regarded as normal variants, do NOT meet reporting criteria. If a clinically significant anomaly is reported, all findings (including those of no individual significance) should be included in the same report. For example, do NOT report an isolated finding of polydactyly (extra fingers or toes) or Mongolian spot in an infant. But if either finding occurred with a major cardiac defect, report all findings in the SAE Report.

⁴ Please ensure that any other protocol-specific reporting requirements are met.

Contact Information for the DAIDS Safety Office: Website: <http://rsc.tech-res.com> - Email: [contact]

Office [contact] (U.S. only) or [contact] – **[contact] (U.S. only) or [contact] (*Office Phone and Fax are accessible 24 hours per day*)

Mailing Address: DAIDS Safety Office [name]

Reporting Adverse Events in an Expedited Manner

The timeframe for expedited reporting of individual AEs begins when the clinical research site recognizes that an event meets SAE criteria for expedited reporting to DAIDS. The day that the site becomes aware of the event is considered Day 1. Clinical research sites must submit AEs to the DAIDS Safety Office immediately, and no later than 3 reporting days after the site becomes aware of an event that meets criteria for expedited reporting.

“Reporting days” are those that count toward the 3-day timeline provided for reporting of EAEs to DAIDS. The criteria used to determine reporting days are as follows:

- A reporting day starts at 12:00 AM (midnight) and ends at 11:59 PM local time.
- A day is counted as a reporting day regardless of the time of day that awareness occurred. The day a site indicates that site personnel became aware of an EAE that meets reporting criteria shall count as day 1 (even if it is 23:00) if that day occurs on a reporting day (i.e., Monday through Friday). If that day occurs on a non-reporting day (i.e., Saturday or Sunday), then the next reporting day shall count as day 1.
- Monday through Friday count as reporting days.
- Saturday and Sunday are not considered reporting days.
- Any holiday (U.S. or in-country/local) that occurs on a Monday through Friday counts as a reporting day. The figure above details EAE reporting requirements. For each PlusPills participant, the EAE reporting period begins with study enrollment (Day 0), and ends with the participant's termination visit. All EAEs should be reported to the DAIDS Regulatory Support Center (RSC) using the internet- based DAIDS Adverse Experience Reporting System (DAERS).

The process of EAE reporting via DAERS involves a designated "Study Reporter" creating an electronic EAE report and a designated "Study Physician" reviewing the EAE report, signing the EAE report with an electronic signature, and submitting the EAE report to the DAIDS RSC. If an EAE report is not completed and submitted within three reporting days of site awareness of the EAE, an explanation must be entered in DAERS before the report can be submitted.

DAERS also may be used to modify or update an EAE report or to withdraw an EAE report that was submitted in error.

DAERS incorporates a report printing function that should be used to print all EAE reports — including modifications and updates — for filing in participant study notebooks. Automated email messages confirming submission of EAE reports also should be printed and filed with the print- out of the associated EAE report.

In the event that DAERS cannot be accessed (e.g., due to poor internet connectivity), paper-based EAE reporting should be used, per instructions provided in the *Manual for Expedited Reporting of Adverse Events to DAIDS*. Completed paper EAE Forms may be faxed or digitally scanned and emailed to the DAIDS RSC via email. The EAE Form and form completion instructions are available on the DAIDS RSC web site (<http://rsc.tech-res.com>). Contact details for submission of EAE Forms to the RSC are provided in the *Manual for Expedited Reporting of Adverse Events to DAIDS*.

IMPORTANT: Sites must submit an AE CRF to DAIDS along with any SAE/EAE. The following data points must be exactly the same on both the AE Log submitted to EAE Report submitted to DAERS:

- Participant ID

- Onset Date
- Severity of event
- Relationship to study product
- Adverse Event Term (Diagnosis)

It is important to remember that if the site updates any of these data points on one document that same change must be made on the other.

16.10 : SELECTED ETHICAL-LEGAL NORMS IN CHILD AND ADOLESCENT HIV PREVENTION RESEARCH IN SOUTH AFRICA: CONSENT, CONFIDENTIALITY AND MANDATORY REPORTING [revised]

Suggested citation: [name] & [name] (2013). Selected ethical-legal norms in child and adolescent HIV prevention research: Consent, confidentiality and mandatory reporting [revised]. NIH, Desmond Tutu HIV Foundation (DTHF) and European and Developing Countries Clinical Trials Partnership (EDCTP): 2013.

Comments to [name] ([contact]) or [name] ([contact]) at the HIV AIDS Vaccines Ethics Group (HAVEG), University of KwaZulu-Natal (UKZN) South Africa
<http://www.saavi.org.za/haveg.htm>

Updated 4 June 2013

INTRODUCTION

The HIV AIDS Vaccines Ethics Group (HAVEG) at the University of KwaZulu-Natal (UKZN) was funded through the European and Developing Countries Clinical Trials Partnership (EDCTP) to develop resources on the ethical-legal framework for researchers and research ethics committees (RECs) working with adolescent HIV prevention trials. This memo was originally designed to assist and guide researchers working on the South African Studies on HIV in Adolescents (SASHA) project. The aim of the SASHA study was to build stakeholder capacity for adolescent prevention trials. The memo has been revised, updated and adapted to assist other protocol developers and protocol reviewers by identifying key ethical-legal issues in adolescent HIV prevention trials and describing the legal obligations relating thereto. Current funding to update this resource is received from the National Institutes of Health via the Desmond Tutu HIV Foundation (DTHF).

Key legal complexities in HIV prevention research with adolescents include:

- Who consents for trial enrolment? Who consents to the health-related interventions in the trial?
- What components of the trial should adolescents enjoy confidentiality for?
- What disclosures are likely to trigger reporting obligations?
- What should researchers do to intervene to assist adolescents when key problems are picked up?

Based on the current ethical-legal framework, this memo has identified nine key norms which should apply to adolescent HIV prevention trials. These are:

1. A parent or legal guardian (LG) should provide consent for adolescents to take part in prevention trials;
2. Adolescents should consent independently to key trial components, even though their parents/ LGs will provide consent to enrolment in the trial;
3. Adolescents should enjoy confidentiality for key trial components;
4. Adolescents' right to confidentiality can be limited and adolescents could be asked to disclose to otherwise confidential information to a trusted adult in certain instances;
5. Parents/ LGs and adolescent should understand what information will or will not be made available to parents/ LGs;
6. If adolescents are being abused, neglected or maltreated, this should be reported to authorities and adolescents should be assisted;
7. If adolescents are engaged in underage sexual relationships that are consensual but exploitative, this should be reported to the authorities and the adolescents should be assisted;
8. There is no legal obligation to report other offenses but adolescents should be assisted; and
9. Parents/ LGs and adolescents should consent to confidentiality limits posed by reporting to authorities.

These are each discussed in more detail below:

1: A parent or legal guardian (LG) must provide consent for adolescents to take part in prevention trials

1. The first norm is that a parent or LG must provide consent for trial enrolment.
2. How was this established? Currently, there is no clear legal standard specifying when children can independently consent to research, however, there are ethical norms. The Department of Health's GCP (2006) guidelines¹ provide that children cannot consent on their own to clinical trials and that consent must be obtained from a parent or a LG. The National Health Research Ethics Council guidelines (2004)² allow that adolescents can only consent unassisted to minimal risk research (where research risks are approximate to those of the child's everyday life). Clinical trials are generally held to present a higher standard of risk than this, therefore, consent from a parent or LG must be secured.
3. Parents or LGs must consent to adolescent enrolment only when they understand the implications for their children and themselves. Some of the norms relating to the manner in which the trial will be run (described in more detail below) may be unacceptable to a parent, for example, the protocol may provide that parents will not necessarily be told that their child is pregnant or that their child elected to have the pregnancy terminated with the assistance of researchers. Therefore, in such situations parents or LGs may refuse to enrol their child in the

trial. Adolescents themselves must provide assent to participation. Some norms may be also unacceptable to an adolescent, for example, the obligation to disclose HIV status to a trusted adult if they test positive. Therefore, adolescents may also refuse to enrol in the study.

4. In the future, if Section 71 of the National Health Act³ is implemented, parental/legal guardian consent will be a legal requirement for *all* health research (trial and non-trial). This change in the law will have very few repercussions in the clinical trial environment, where stakeholders are generally used to this requirement. However, repercussions will be felt by social scientists. In addition, should s71 be implemented then children will be required to “consent” rather than assent alongside their parent if they have “sufficient understanding”.

2: Adolescents should consent independently to key trial components, even though their parents or LGs will provide consent to trial enrolment

1. The second norm is that even where a parent or LG provides consent for enrolment, adolescents should consent independently to certain trial components.
2. How was this norm established? According to various statutes, adolescents can consent independently to a number of health-related interventions, such as:
 - a. **Terminations of Pregnancy** at any age (s 5, Choice of Termination of Pregnancy Act, No. 92 of 1996)⁴. However the Act requires providers to advise adolescents to “consult with their parents, guardian, family members or friends” before the termination (s 5, Choice of Termination of Pregnancy Act)⁴
 - b. **HIV testing** from the age of 12 (s 130, Children’s Act, No. 38 of 2010)⁵ and even children below 12 can consent independently to such testing if they have “sufficient capacity”
 - c. **Medical treatment** from the age of 12, including STI and HIV treatment provided the child has “sufficient maturity”. In other words the child should be 12 and have the mental capacity to understand the benefits, risks, social and other implications of the treatment; and (s 129, Children’s Act No. 38 of 2010)⁶
 - d. **Contraceptives** and contraceptive advice, including emergency contraceptives from the age of 12 (s 134, Children’s Act, No. 38 of 2010)⁷
 - e. **Circumcision** at the age of 16⁸. If boys are below the age of 16, then consent must be obtained from their parent or legal guardian. The Act also requires that boys below 16 can only be circumcised for ‘religious’ or ‘medical reasons on the recommendation of a medical practitioner’ whereas those above 16 may undergo circumcision for any reason. Boys over 16 must receive counselling prior to the circumcision, and they have the right to refuse circumcision. (s12 (8) and s12(9-10) of the Children’s Act No. 38 of 2005

- f. **Surgical operations** at the age of 12 provided he/she (i) has 'sufficient maturity and has the mental capacity to understand the benefits, risks, social and other implications of the surgical operation', and (ii) is assisted by a parent or guardian. (See section 129(3) of the Children's Act No. 38 of 2005).

3. Another factor that is relevant to consent by adolescents within HIV prevention trials is the age at which they **can lawfully engage in sex**. This is set at 16 in the Sexual Offences Act (s 15, Criminal Law (Sexual Offences and Related Matters) Amendment Act, No, 32 of 2007). See section 7 for more detail.
4. Currently in prevention trials this means that:
 - a. Adolescents, who need to be tested for pregnancy regularly as part of a prevention trial, can give their own consent for pregnancy tests from the age of 12 and could receive a TOP at any age with their own consent, provided they have the capacity to consent;
 - b. Adolescents, who need to be tested for HIV regularly as part of the study, can give their own consent for these HIV tests from 12;
 - c. Adolescents, who need to be tested regularly for STIs, can give consent on their own from 12 for STI testing and treatment, if required, provided they meet the capacity requirements (which could vary according the medical condition or procedure); and
 - d. Adolescents wanting access to male or female condoms or other forms of contraceptives or contraceptive advice could receive these on their own from the age of 12.

3: Adolescents should enjoy confidentiality for key trial components

1. The third norm is that adolescents should enjoy confidentiality for key trial components. How was this norm established?
2. Firstly, adolescents have the right to confidentiality for the range of health-related interventions that they have consented to independently. That is:
 - a. Adolescent TPs of 12 years and older (and not their parents) should receive HIV test results;
 - b. Adolescents of 12 (who have capacity) and older (and not their parents) should get the results of STI tests;
 - c. Adolescent TPs of 12 years and older should enjoy confidentiality for access to contraceptives;
 - d. Adolescent TPs (and not their parents) should get results of pregnancy tests and/ or enjoy confidentiality for TOPs.
3. Secondly, adolescents have a right to privacy if there is an expectation of privacy that society regards as reasonable. Where the law is silent on whether a right to privacy exists, one can use the "legitimate expectation test" to establish if something should be kept private.

- a. It can be argued that adolescents who are 16 years and older have the right to confidentiality regarding their sexual risk data. That is, older adolescents (and not their parents) should get the results of sexual risk assessments. This is on the grounds that older adolescents would have an expectation of privacy (which most would hold as reasonable) because adolescents can lawfully consent to sex at 16. For adolescents who are under 16, the above rationale may not hold, however, parents can agree not to be informed on the grounds that safeguards (such as counseling and access to services) will be built in to the trial.

4: Adolescents' right to confidentiality can be limited and adolescents could be asked to disclose otherwise confidential information to a trusted adult in certain instances

1. The fourth norm is that even though adolescents have rights to confidentiality, these rights can be limited.
2. How was this norm established? In law, a child's right to confidentiality regarding their health status can be limited where this is in their "best interests" (s 13(1)(d), Children's Act). In ethics, respect for emerging autonomy can be balanced by the need to minimize harms and promote welfare. In law, South African courts have generally held that the best interests of children require a wide range of factors to be considered in decision-making, including those which promote a child's physical, moral, emotional and spiritual welfare.⁹ This means decision-makers must evaluate, weigh and balance these competing factors. They must also take into account the child's wishes.
3. In prevention trials, adolescents, who acquire conditions or a health status with long-term complications that need on-going support, should be asked to disclose to a trusted adult within a reasonable time-frame, because this is in their best interests. For example, maintaining confidentiality regarding a child's HIV status or their pregnancy may not be in their best interests as these are chronic, long-term conditions that require specialist treatment and emotional support.

5: Parents/ LGs and adolescents should understand what information will or will not be made available to parents/ LGs

1. The fifth norm is that both parties must understand what information will be kept confidential and what will be disclosed to another party.
2. How was this norm established? In law, consent is valid only if it is based on a full appreciation of information that most people would consider very important to know. In ethics, consent is only meaningful if it is based on a full understanding of the personal implications of research participation. In prevention trials, it is possible that the parent/ guardian may refuse enrolment when they understand these matters, or the child may refuse to take part.

6: If adolescents are being abused or neglected, this should be reported to authorities and adolescents should be assisted

1. The sixth norm is that adolescents' right to confidentiality is expressly limited where they are being abused or neglected, or are identified as being in need of care and protection.
2. How was this norm established? In terms of s 110 of the Children's Act (2010)¹⁰ there is a broad range of persons who **must** report any child that has been sexually abused, deliberately neglected or abused in a manner causing physical injury.
3. The category of persons who must report such abuses includes medical practitioners, nurses, psychologists, social service professionals, social workers and members of staff or volunteer workers at a drop-in centres or child and youth care centres.
4. Reports must be made to designated child protection organisations, the provincial department of social development or police officials. While all research staff are not expressly included in this list, some members of the team will fall into these designated categories and are obliged to report.
5. Even if staff do not fall within a designated category obliging them to report, the Act also states that any person who, on reasonable grounds, believes that a child is in need of care and protection **may** report that belief to the provincial department of social development, a designated child protection organisation or a police official.
6. In addition, researchers should assist children by referring them for various kinds of support. Assistance could involve encouraging adolescents to reach out for all forms of adult support, including their reaching out to their parents, where this seems helpful.
7. Trial sites could partner with professional organisations to assist them to make determinations of abuse or neglect.

7: If adolescents are engaged in underage sexual relationships that are consensual but exploitative, this should be reported to the authorities and the adolescents should be assisted

1. The seventh norm is that adolescents' right to confidentiality may be expressly limited in certain circumstances, such as when certain sexual offences are being committed.
2. How was this norm established? In ethics, respect for emerging autonomy can be balanced by the need to minimize harms and promote welfare. In law, the Criminal Law [Sexual Offences and Related Matters] Amendment Act, No. 32 of 2007¹¹ requires any person who is aware of a sexual offence having been committed against a child to report this to the South African Police Service (SAPS).
3. This memo recommends that all instances the sexual offences of rape and commercial sex work should be reported to SAPS. In terms of rape, it is important to note that all sex (even if it is 'consensual') with persons under the age of 12 is rape in terms of the Sexual Offences Act. Therefore, even if a child participant discloses 'consensual' sex under 12, this will have to be reported as statutory rape.
